7.3 Ocular tolerance assessment by the investigator

Ocular tolerance by the investigator assessed on a 4-point ordinal scale (Very satisfactory / Satisfactory / Not very satisfactory / Unsatisfactory) will be presented by frequency distribution for each modality and frequency distribution after regrouping 'very satisfactory' with 'satisfactory', and 'not very satisfactory' with 'unsatisfactory'.

Ocular tolerance assessment will be described at each assessment time (D14 and D42).

7.4 Ocular tolerance assessment by the patient

Ocular tolerance by the patient assessed on a 4-point ordinal scale will be presented by frequency distribution for each modality and frequency distribution after regrouping 'very satisfactory' with 'satisfactory', and 'not very satisfactory' with 'unsatisfactory'.

Ocular efficacy assessment will be described at each assessment time (D14 and D42).

7.5 Ocular and systemic adverse events

Ocular and systemic AEs reported during the investigation will be coded with MedDRA 21.1, September 2018 (English). Ocular and systemic AEs will be analysed separately on the basis of the localisation as recorded by the investigator in the CRF.

Summary tables will be performed on treatment-emergent AEs (TEAEs). Non TEAEs will be described in individual patient data listings. TEAEs are AEs that occurred the same day or after the first IP administered. AEs that occurred the day of the first IP administered will be reviewed during a blind review meeting to decide if they have to be considered as TEAE or not.

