9.3 Procedures for collection, registration and notification of adverse events

9.3.1 Definitions

9.3.1.1 Definition of adverse event (AE)

Adverse Event (AE): any untoward medical events that occurs in a patient who has accepted the participation in the study and which does not necessarily have a causal relationship with the Investigational Product (IP).

An AE can therefore be any unfavourable and unintended sign (including abnormal laboratory finding), symptom, or disease temporally associated with the use of an IP, whether or not related to the product.

An AE may include, but is not limited to:

- A new illness
- Worsening of a sign or symptom of the condition under treatment or of a concomitant illness
- An effect of the IP (Test product or comparator product)
- An effect of an auxiliary product
- Event unrelated to participation in the clinical study
- A combination of one or more of these factors

Adverse Drug Reaction (ADR): untoward and unintended response in a patient to the IP which is related to any dose administered to that patient.

Unexpected ADR: An adverse reaction is unexpected when the nature and severity is not consistent with the information about the medicinal product set out in the investigator's brochure relating to the trial in question.

All AEs, including intercurrent illnesses, occurring during the study will be documented in the e-CRF. Concomitant illnesses, which existed prior to entry into the study, will not be considered AEs unless they worsen during the treatment period. Pre-existing conditions will be recorded in the CRF.

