9.3.2 Documentation and notification

9.3.2.1 Documentation and reporting of Adverse Events / Reactions

The principal investigator shall:

- a) record in the CRF every **adverse event** and adverse reaction, together with an assessment,
- b) adverse event reporting will extend from signing of informed consent until the final study visit.
- c) report to the sponsor, without unjustified delay, all serious adverse events and reactions; this information shall be promptly followed by detailed written reports,
- d) supply the sponsor, upon sponsor's request, with any additional information related to the safety reporting of a particular event.

All AEs, regardless of the relationship to the investigational product, will be recorded in the CRF.

All AE reports should contain: **a brief description of the event, localization, date and time of onset, duration (hours or days), intensity of symptoms (severity), treatment required, relationship with IP and protocol procedure, action taken with the IP, outcome, date and time of resolution and whether the event is classified as serious.**

LABORATOIRES THEA	Protocol # LT2769-001/ 17E1044	Final Version 2.0 Date: 13/11/2017	Confidential Page 55/75
-------------------	--------------------------------	---------------------------------------	----------------------------

All AEs experienced by a patient, irrespective of the suspected causality, will be monitored until the event has resolved, any abnormal laboratory values have returned to baseline or stabilised at a level acceptable to the investigator and Medical expert, until there is a satisfactory explanation for the changes observed, or until the patient is lost to follow-up.

9.3.2.2 Documentation and reporting of Serious Adverse Event by the investigator to the sponsor

In case of Serious Adverse Event, the Investigator must:

1. Complete the relevant CRF pages and the SAE form with all available initial information

Immediately scan and send out the completed SAE form to the

[contact] whilst copying the field CRA of the CRO.

If it is not possible, please fax this SAE form to: **[contact]**

2. **Within 24 hours**, send the completed original SAE form duly completed to the following address by mail:

GlobalSafety and MedInfo Department

Laboratoires théa

[name]

[name]

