4.3.17 Adverse event (AE) time to occurrence

Time to AE occurrence (days) will be calculated as follows:

Date of onset – Date of IP first instillation.

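### The treatment-emergent definition in SAP 7.5 has no worsening clause, so an adverse event that starts in the saline run-in and worsens on T2769 can be missing from the AE summary tables

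*SAP*

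**What the plan says.** - **Definition.** SAP 7.5: "TEAEs are AEs that occurred the same day or after the first IP administered". The AE summary tables are built on these treatment-emergent AEs (TEAEs). For the rest, "Non TEAEs will be described in individual patient data listings".
- **Exception for the first day.** SAP 7.5 adds that "AEs that occurred the day of the first IP administered will be reviewed during a blind review meeting". No similar review is planned for events with an earlier onset.
- **Dating.** SAP 4.3.17 computes time to AE occurrence as "Date of onset – Date of IP first instillation".
- **Collection window.** Protocol 9.3.2.1: "adverse event reporting will extend from signing of informed consent until the final study visit". The saline run-in, from D-14/D-10 to D1, is therefore covered.
- **Worsening.** Protocol 9.3.1.1 includes among AEs "Worsening of a sign or symptom of the condition under treatment or of a concomitant illness". It also says: "Concomitant illnesses, which existed prior to entry into the study, will not be considered AEs unless they worsen during the treatment period".
- **Planned summaries.** Protocol 12.3.3 summarises patients with at least one event for all AEs, product-related AEs, serious AEs and AEs leading to withdrawal, with no limit to TEAEs. SAP 8 does not mention the narrowing.

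**The concern.** A study with a run-in on an auxiliary product will usually have some AE records that open before the first dose of the investigational product. A TEAE definition should say what happens when such an event gets worse on treatment, and this one does not. Read literally, an ocular event that is mild five days before D1, becomes severe on D10, is rated related to T2769 and leads to withdrawal would still be non-TEAE if it sits on one record with its run-in onset date.

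Safety is the only secondary objective and there is no control arm, so the AE percentages are read at face value. The events at risk are those in which T2769 may have aggravated a problem that began on saline. Leaving them out can only make the product look better tolerated.

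**Working it through.** The plan gives no rate for run-in AEs or for their worsening, so there is no stated figure to reproduce. The check is a reading of the text, followed by a scale for the effect.

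**1. Does 'occurred' mean onset?** SAP 4.3.17 measures occurrence from the onset date. A run-in AE then has a negative time to occurrence and fails the SAP 7.5 test.

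**2. Can run-in AE records exist?** Yes. Reporting starts at consent, AEs are collected at D1 (Protocol 5.4.2 and 9.2), and Protocol 9.3.1.1 names an effect of an auxiliary product as a possible AE. The SAP's own non-TEAE category presupposes them.

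**3. Does the worsening get its own onset date?** The documents do not settle this.
- *Pointing to a new record:* Protocol 9.3.1.1 makes worsening an AE in its own right. Entered that way, it has an on-treatment onset and is a TEAE.
- *Pointing to one continuing record:* Protocol 9.3.2.1 asks for onset, intensity, outcome and resolution for each event and has it monitored until resolved. SAP 4.3.18 computes duration from onset to recovery. SAP 7.5.3 lists one onset and one severity.
- *Unclear:* the Protocol 9.3.1.1 rule on prior illnesses turns on study entry, which is not defined there. Inclusion takes place at D1 (Protocol 5.4.2), but SAP 2.1 ties enrolment to consent and the screening visit.

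**4. Consequence under each convention.**

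| Recording convention | TEAE under SAP 7.5? | Tables 5.11 to 5.26 | Listings |
|---|---|---|---|
| Worsening opens a new record | Yes | Counted | Shown |
| Original record kept | No | Not counted | Shown |

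**5. Size per patient.** Planned n = 55 (Protocol 6.4, SAP 1.5), so one patient is 1/55 = 1.8 percentage points. For scale, the Wilson formula of SAP 3 with z = 1.96 gives:
- 0/55: 0.0% to z²/(n + z²) = 3.8416/58.8416 = 6.5%
- 1/55: 0.3% to 9.6%
- 2/55: 1.0% to 12.3%

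**6. How many patients? (assumptions only)**
- *Incidence.* Protocol 3.4 quotes ocular AE incidences of 1.9% and 13.2% in the two arms of an earlier study. Its length is not given, so T = 28 to 84 days is assumed.
- *Run-in cases.* With a constant hazard, the expected number over d days is 55 × [1 − (1 − p)^(d/T)].
  - Low: p = 0.019, T = 84, d = 10 gives 0.13 patients.
  - High: p = 0.132, T = 28, d = 14 gives 55 × (1 − √0.868) = 3.76 patients.
- *Worsening on T2769.* If 10% to 50% worsen (assumed), the range is 0.13 × 0.1 = 0.01 to 3.76 × 0.5 = 1.88 patients.
- *Sensitivity of the upper end.* With T = 56 or 84 days it falls to 0.96 or 0.64 patients.
- *Cruder alternative.* If 2% to 10% of patients have a run-in AE of any kind and 10% to 50% of those worsen, the range is 55 × 0.02 × 0.1 = 0.11 to 55 × 0.10 × 0.5 = 2.75 patients.

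At the quoted incidences the whole ocular AE result would rest on about 55 × 0.019 = 1.0 to 55 × 0.132 = 7.3 patients, so even one omission would be noticeable.

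**The case against.** A reader might infer that every run-in event that worsens is certain to be dropped and that the safety result is therefore undercounted. The documents do not support that. Protocol 9.3.1.1 counts worsening as an AE, and a site that opens a new record loses nothing. For the dry eye symptoms graded in this trial, such as burning/irritation, that route is especially natural. The convention may be set in the CRF or the data management plan, which are not among the documents reviewed. This part of the objection stands and makes the loss conditional.

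Three further limits also stand:
- Emergence is not decided by onset date in every case, because first-day events go to a review meeting.
- The AE percentages are not the whole safety result. SAP 1.3.4 also lists instillation symptoms, visual acuity and two tolerance ratings.
- An affected patient does not vanish. A withdrawal appears in the discontinuation table and listing (SAP 5.1), and the AE listings show treatment emergence, severity, relationship and action taken (SAP 7.5.3).

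The figures in step 6 also ignore run-in events that resolve before D1 and patients found ineligible at D1. Both would lower the number.

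None of this closes the gap. A listing does not enter a percentage, the first-day review does not reach earlier onsets, and the three centres named in SAP 3.1 could follow different conventions.

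**Conclusion.** The point holds as a gap in the definition with a conditional consequence. SAP 7.5 has no worsening clause, and whether a run-in AE that worsens on T2769 is counted depends on a recording convention that neither document states. If the original record is kept, the event is missing from the AE tables, although Protocol 12.3.3 would have summarised it and SAP 8 does not declare the change.

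The number affected cannot be derived from the documents. Under the assumptions above it lies between almost none and two or three patients, and is probably at the low end. The direction is certain even though the size is not: for events that worsen on T2769, the counts can only be too low.

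**What to change.** - **SAP 7.5.** Define TEAEs as AEs that start on or after the first IP instillation, or that start before it and worsen in severity or become serious on or after it. Apply this to Tables 5.11 to 5.26.
- **SAP 4.3.17.** For the second group, count time to occurrence from the date of worsening.
- **Data.** Query the run-in AEs still open at D1 where the date of worsening or the later severity is not recorded.
- **SAP 8.** List the restriction of AE summaries to TEAEs as a change from Protocol 12.3.3.

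The definition should not extend to run-in AEs merely because they are rated related or lead to withdrawal. That would count events that never worsened and would leave them without a date of worsening.

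The cost is a small text change, one programming condition, a few data queries and possibly a slightly higher TEAE count. If the sites already open new records for worsening, no count changes.

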7.5.1 Summary of adverse events

Separate summaries of treatment-emergent ocular and systemic AEs will be performed presenting the number and percentages of patients experiencing at least one:

- AE,
- Serious AE (SAE),

- Drug-related AE (i.e. related or missing relationship with the IP),
- Drug-related SAE (i.e. related or missing relationship with the IP),
- AE leading to premature study withdrawal.

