12.3.3 Safety Analyses

Safety endpoints will be analysed in the Safety Set.

Safety analysis will be based on the following criteria:

- Ocular symptoms upon instillation: : burning/irritation, stinging/eye pain, itching/pruritus, eye dryness feeling, foreign body sensation, and other symptoms will be graded by the patient.at D14 and D42
- Far best corrected visual acuity assessment at D42
- Global ocular tolerance assessed by the investigator at D42
- Global ocular tolerance assessed by the patient at D42
- Ocular and systemic adverse events (AE)

The adverse events will be coded using the MedDRA dictionary and described according to MedDRA Preferred Term (PT) and primary System Organ Class (SOC).

The number and percentage of patients with at least one adverse event will be summarized for all AEs, study product-related AEs, serious AEs, and AEs leading to study withdrawal.

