7 SAFETY ANALYSIS

Safety endpoints will be analysed on the Safety set.

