7.5.3 Individual listing of adverse events

Individual patient data listings of AEs will be performed for AEs, SAEs and drug-related SAEs, separately for ocular and systemic AEs. The following variables will be presented:

- Patient's identifier,
- Gender,
- Age at baseline,
- Investigator's reported term,
- SOC,
- PT,
- Localisation,
- Date / Time of onset,
- Time to onset (days) from the date of the first IP instillation,
- Treatment-emergence,
- Date/Time of recovery / Date of death, if any,
- Duration (days),
- Outcome,
- Frequency and details,
- Severity,
- Action taken regarding the IP,
- Requirement for therapy adjustment/modification,
- Requirement for surgical / medical procedure and details,
- Seriousness,
- Relationship with the IP in the investigator's opinion and details,
- Relationship with protocol procedure and details.

Listings will be sorted by patient's identifier and date of onset.

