Table 4.128 Analysis of Mean TBUT (seconds) – Change from baseline at D14 and D42 – Student – Observed data – Contralateral Eye – PP set

Table 4.1129 Ocular efficacy assessment by the investigator – PP set

5. Safety analysis

Table 5.1 Summary of Ocular symptoms upon instillation– Burning/Irritation – Safety set

Table 5.2 Summary of Ocular symptoms upon instillation – Stinging/Eye pain – Safety set

Table 5.3 Summary of Ocular symptoms upon instillation – Itching/Pruritus – Safety set

Table 5.4 Summary of Ocular symptoms upon instillation – Eye dryness feeling – Safety set

Table 5.5 Summary of Ocular symptoms upon instillation – Foreign body sensation – Safety set

Table 5.6 Summary of Total score of ocular symptoms upon instillation – Safety set

Listing 5.1 Listing of data relative to other ocular symptoms upon instillation – Safety set

Table 5.7 Summary of FBCVA – Worse eye – Safety set

Table 5.8 Summary of FBCVA – Contralateral eye – Safety set

Table 5.9 Ocular tolerance assessment by the investigator – Safety set

Table 5.10 Ocular tolerance assessment by the patient – Safety set

Table 5.11 Overview of treatment-emergent ocular adverse events – Safety set

Table 5.12 Summary of treatment-emergent ocular AEs per SOC and PT – Safety set

Table 5.13 Summary of treatment-emergent ocular SAEs per SOC and PT – Safety set

Table 5.14 Summary of treatment-emergent ocular drug-related AEs per SOC and PT– Safety set

Table 5.15 Summary of treatment-emergent ocular drug-related SAEs per SOC and PT – Safety set

Table 5.16 Summary of treatment-emergent ocular AEs leading to premature withdrawal per SOC and PT – Safety set

Table 5.17 Summary of treatment-emergent ocular AEs per SOC, PT and severity – Safety set

Table 5.18 Summary of treatment-emergent ocular AEs per SOC, PT and relationship to the IP – Safety set

Table 5.19 Overview of treatment-emergent systemic adverse events – Safety set

Table 5.20 Summary of treatment-emergent systemic AEs per SOC and PT – Safety set

Table 5.21 Summary of treatment-emergent systemic SAEs per SOC and PT – Safety set

Table 5.22 Summary of treatment-emergent systemic drug-related AEs per SOC and PT– Safety set

Table 5.23 Summary of treatment-emergent systemic drug-related SAEs per SOC and PT – Safety set

Table 5.24 Summary of treatment-emergent systemic AEs leading to premature withdrawal per SOC and PT – Safety set

Table 5.25 Summary of treatment-emergent systemic AEs per SOC, PT and severity – Safety set

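### Every adverse-event table in the SAP is ocular-only or systemic-only, so none gives the once-per-patient counts promised in Protocol 12.3.3, and SAP section 8 does not declare the change

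*SAP*

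**What the plan says.** Protocol 12.3.3 sets the commitment: "The number and percentage of patients with at least one adverse event will be summarized for all AEs, study product-related AEs, serious AEs", and it adds events leading to study withdrawal. Nothing in that sentence divides the counts by localisation.

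SAP 7.5 introduces the division: "Ocular and systemic AEs will be analysed separately on the basis of the localisation as recorded by the investigator in the CRF". It also confines the summary tables to treatment-emergent events. SAP 7.5.1 then specifies the overview: "Separate summaries of treatment-emergent ocular and systemic AEs will be performed presenting the number and percentages of patients experiencing at least one" event in each of five rows (any, serious, drug-related, drug-related serious, leading to withdrawal). SAP 7.5.2 applies the same split to the tables by system organ class (SOC) and preferred term (PT). Appendix 2 carries this through. The ocular overview is Table 5.11. Its counterpart, Table 5.19, is titled "Overview of treatment-emergent systemic adverse events".

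For events before the first dose, SAP 7.5 says: "Non TEAEs will be described in individual patient data listings". SAP 7.5.3 describes those outputs: "Individual patient data listings of AEs will be performed for AEs, SAEs and drug-related SAEs, separately for ocular and systemic AEs". On the population, SAP section 7 says: "Safety endpoints will be analysed on the Safety set".

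SAP section 8 lists seven changes from the protocol. The split of the adverse-event summaries is not one of them.

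**The concern.** Safety is the only secondary objective of the trial. The share of patients with any adverse event, any related event or any serious event is the basic summary a reader looks for. The protocol promises those shares as single figures. The SAP replaces each with a pair of figures for groups of patients that may overlap, and the planned tables do not show how large the overlap is.

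If the SAP is followed as written, the report will contain no table that answers the protocol's question. The reader will have to guess, or someone will be tempted to add two percentages that do not add. Because section 8 is silent, the omission would also not be flagged as a deviation from the protocol.

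**Working it through.** **Step 1. Compare the commitment with the planned outputs.**

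| | Protocol 12.3.3 | SAP 7.5.1, 7.5.2 and Appendix 2 |
|---|---|---|
| Unit | patients with at least one event | patients with at least one event |
| Localisation | no split | ocular and systemic separately |
| Categories | any, related, serious, withdrawal | the same four, plus related serious |
| Population | Safety set | Safety set |

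Appendix 2 has 16 adverse-event tables. Tables 5.11 to 5.18 (8) are ocular and Tables 5.19 to 5.26 (8) are systemic. That is 8 + 8 = 16, which leaves no combined table.

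**Step 2. Ask whether the split tables determine the combined count.** Let o be the number of patients with an ocular event, s the number with a systemic event, b the number with both, and N the size of the Safety set. Then

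any = o + s − b.

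The tables give o and s but not b. Since b lies between max(0, o + s − N) and min(o, s),

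max(o, s) ≤ any ≤ min(N, o + s).

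The two bounds coincide only when one count is zero, or in the extreme case where one count equals N. The latter is not realistic here.

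**Step 3. Put in numbers.** The documents give no expected event counts, so o and s are assumptions. N = 55 is the planned enrolment (Protocol 6.4, SAP 1.5), used in place of the Safety set.

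| o | s | Lower bound | Upper bound |
|---|---|---|---|
| 4 | 0 | 4 (7.3%) | 4 (7.3%) |
| 3 | 3 | 3 (5.5%) | 6 (10.9%) |
| 5 | 5 | 5 (9.1%) | 10 (18.2%) |
| 6 | 5 | 6 (10.9%) | 11 (20.0%) |
| 8 | 6 | 8 (14.5%) | 14 (25.5%) |
| 10 | 10 | 10 (18.2%) | 20 (36.4%) |

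For the 6 and 5 case: max(6, 5)/55 = 6/55 = 10.9%, and (6 + 5)/55 = 11/55 = 20.0%. When o = s, the upper bound is twice the lower. The first row shows the ambiguity disappearing when one count is zero.

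**Step 4. Check the listings.** SAP 7.5.3 lists adverse events with patient identifier, localisation, treatment-emergence, seriousness and relationship. SAP 5.1 adds a listing of discontinuations with the detailed reason. Matching the ocular and systemic listings on patient identifier gives b, so the combined count can be derived. However, Appendix 2 names only Listings 1.1 to 1.4, 4.1, 4.2 and 5.1. None of these is an adverse-event listing, and 7.5.3 states no population for those it describes.

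**The case against.** The best defence is that nothing is lost. About 55 patients are expected, the identifiers are in the listings, and counting each patient once is a short task. Protocol section 12 leaves detailed methods to the SAP, and Protocol 12.3.3 itself names the criterion as ocular and systemic events. The documents also suggest that the ambiguity may be small in some rows. Protocol 3.4 reports no serious event in two cited earlier studies and expects only ocular product effects, so the serious and related rows may well have a zero on one side. All of this limits the size of the problem. It does not supply the missing figure: the commitment is to a summary of patients, and the plan contains no table with that summary.

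Several stronger readings are tempting, but the documents do not support them:

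- *The protocol's figures cannot be produced.* They can, from the data and the 7.5.3 listings. They are simply not planned as output.
- *Run-in events vanish.* Protocol 9.3.2.1 says "adverse event reporting will extend from signing of informed consent until the final study visit", so these events are collected. SAP 7.5 and 7.5.3 send them to listings that carry a treatment-emergence variable. The absence of those listings from Appendix 2 is a clerical mismatch. The contraception listing promised in SAP 5.2 is missing from it too.
- *The limit to treated patients is an undeclared change.* Protocol 12.2 and 12.3.3 already set the Safety set as the safety population, so the SAP changed nothing here.
- *The limit to treatment-emergent events is a clear departure.* Protocol 5.1.3.3 frames the adverse-event criterion around the 42-day treatment period, so summarising those events and listing the rest is a fair reading.

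**Conclusion.** The point stands in a narrow form. The protocol promises patient counts without a split by localisation, the SAP tabulates them only with one, and section 8 does not say so. Unless one of the two counts is zero, the planned tables leave the any-event figure undetermined. In the illustration with 6 and 5 patients of 55, the range is 10.9% to 20.0%.

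The illustration rests on assumed counts and on 55 as denominator. The absence of a combined table rests on neither. The row most likely to be affected is the one for any event. The primary analysis is untouched, and no safety data are lost.

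**What to change.** Add to SAP 7.5.1 and to Appendix 2 one combined overview table on the Safety set. It should count each patient once whatever the localisation, with rows for any, drug-related, serious, drug-related serious and withdrawal-leading treatment-emergent events. Keep the ocular and systemic tables as they are. A combined table by SOC and PT is optional. If the sponsor prefers not to add the combined overview, section 8 should declare and justify that choice.

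As housekeeping, add the 7.5.3 adverse-event and serious-adverse-event listings to Appendix 2 and state their population, because events before the first dose are reported only there.

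The cost is one extra table and minor SAP edits. All the variables are already collected, and nothing in the design or conduct of the trial changes.
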